6.4. Changes from Protocol-Specified Efficacy Analyses

The primary analysis specified in the protocol Section 8.2.2 and the final analysis will be combined into one final analysis due to early study closure with smaller than planned sample size.

7. SAFETY ANALYSES

7.1. Adverse Events and Deaths

7.1.1. Adverse Event Dictionary

Clinical and laboratory AEs will be coded using the current version of MedDRA. System organ class (SOC), high-level group term (HLGT), high-level term (HLT), preferred term (PT), and lower-level term (LLT) will be provided in the AE dataset.

7.1.2. Adverse Event Severity

The severity of AEs will be graded using the Division of AIDS (DAIDS) Table for Grading the Severity of Adult and Pediatric Adverse Events, Version 2.1 dated July 2017. For each episode, the highest grade attained should be reported as defined in the grading scale. The DAIDS scale is available at the following location:

<https://rsc.niaid.nih.gov/sites/default/files/daidsgradingcorrectedv21.pdf>

Adverse events are graded by the investigator as Grade 1 (mild), Grade 2 (moderate), Grade 3 (severe), Grade 4 (life threatening) or Grade 5 (fatal) according to toxicity criteria specified in the document above. The severity grade of events for which the investigator did not record severity will be left as “missing” for data listings.

7.1.3. Relationship of Adverse Events to Study Drug

Related AEs are those for which the investigator selected “Related” on the AE CRF to the question of “Related to Study Treatment.” Relatedness will always default to the investigator’s choice, not that of the medical monitor. Events for which the investigator did not record relationship to study drug will be considered related to study drug for summary purposes. However, by-participant data listings will show the relationship as missing.

7.1.4. Serious Adverse Events

Serious adverse events (SAEs) will be identified and captured as SAEs if the AEs met the definitions of SAEs that were specified in the study protocol. SAEs captured and stored in the clinical database will be reconciled with the SAE database from the Gilead Global Patient Safety (GLPS) Department before data finalization.

7.1.5. Treatment-Emergent Adverse Events

7.1.5.1. Definition of Treatment-Emergent Adverse Events

Treatment-emergent adverse events (TEAEs) are defined as 1 or both of the following:

- Any AEs with an onset date on or after the study drug start date and no later than 30 days after permanent discontinuation of study drug
- Any AEs leading to premature discontinuation of study drug.

7.1.5.2. Incomplete Dates

If the onset date of the AE is incomplete and the AE stop date is not prior to the first dosing date of study drug, then the month and year (or year alone if month is not recorded) of onset determine whether an AE is treatment emergent. The event is considered treatment emergent if both of the following 2 criteria are met:

- The AE onset date is the same as or after the month and year (or year) of the first dosing date of study drug, and
- The AE onset date is the same as or before the month and year (or year) of the date corresponding to 30 days after the date of the last dose of study drug

An AE with completely missing onset and stop dates, or with the onset date missing and a stop date later than the first dosing date of study drug, will be considered treatment emergent. In addition, an AE with the onset date missing and incomplete stop date with the same or later month and year (or year alone if month is not recorded) as the first dosing date of study drug will be considered treatment emergent.

7.1.6. Summaries of Adverse Events and Deaths

TEAEs will be summarized based on the Safety Analysis Set.

A brief, high-level summary of the number and percentage of participants who experienced at least 1 TEAE in the categories described below will be provided by treatment group. Treatment-emergent deaths observed in the study will also be included in this summary.

Treatment-emergent death refers to deaths that occurred between the first dose date and the last dose date plus 30 days (inclusive).

The number and percentage of participants who experienced at least 1 TEAE will be provided and summarized by SOC, High level term (HLT), PT, and treatment group.

For other AEs described below, summaries will be provided by SOC, PT, and treatment group:

- TEAEs with Grade 3 or higher
- TE study drug-related AEs
- TE study drug-related AEs with Grade 3 or higher
- TE SAEs
- TE study drug-related SAEs
- AEs leading to premature discontinuation of study drug

Multiple events will be counted only once per participant in each summary. Adverse events will be summarized and listed first in alphabetic order of SOC (and HLT within each SOC if applicable), and then by PT in descending order of total frequency within each SOC. For summaries by severity grade, the most severe grade will be used for those AEs that occurred more than once in an individual participant during the study.

In addition to the above summary tables, all TEAEs, TEAEs with Grade 3 or higher, TE study drug-related AEs, TE study drug-related AEs with Grade 3 or higher, and TE SAEs will be summarized by PT only, in descending order of total frequency.

The above summary tables may also be provided for one or more of the following subgroups: kidney disease status (as defined in Section 3.4), high-flow oxygen requirement (Yes, No), and/or region (US, ex-US).

In addition, data listings will be provided for the following:

- All AEs
- All study drug-related AEs
- All AEs with severity of Grade 3 or higher
- All SAEs
- All study drug-related SAEs
- All Deaths
- AEs leading to premature discontinuation of study drug

Listing of renal and hepatic adverse events will be provided. Hypersensitivity including infusion-related reactions adverse events will also be summarized and listed (See [Appendix 2](#)).

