8.2.1.1. Data Monitoring Committee Analysis (Safety Analysis)

The first DMC meeting will be based on data collected after the first 100 participants complete the Day 29 assessment and will include safety data, including renal and hepatic toxicity. No formal efficacy evaluations are planned for this meeting.

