The binary indicator variable (cnsr) with a value of 0 indicates the time to the event of interest is complete or 1 indicates the time to the event is censored.

26) Competing risk analysis

The following SAS code will be used to generate the cause-specific hazard ratio and 95% confidence intervals for the competing risk analysis:

```
proc phreg;
  class trt strat1 strat2 strat3;
  model aval* cnsr (1, 2) = trt strat1 strat2 strat3 / rl;
  hazardratio "Cause-specific hazard" trt;
run;
```

where $cnsr = 0$ if the participant had the event; $cnsr = 2$ if the participant died prior to having the event, and $cnsr = 1$ if the participant did not have the event and did not die.

SAS codes to obtain a cumulative incidence function plot and dataset for further processing for time to first event table:

```
proc lifetest outcif=outcif plots=cif;
  strata trt;
  time aval* cnsr (1) / failcode = 0; *Note: this produces data for the event of interest only;
run;
```

SAS code to obtain support tables:

```
proc univariate;
  by trt cnsr;
  var aval;
  output pctlpre=P_ min=min max=max pctlpts= 10, 25, 50, 75, 90;
run;
```

27) SAS code for stratified 2-sided Wilcoxon Rank sum test (stratified on baseline result)

```
proc freq;
  table base*trt*aval/cmh2 scores=modriddit;
run;
```

where BASE is the baseline value.

28) SAS code for ANCOVA:

```
ods output ParameterEstimates=out1 LSMeans=out2 LSMeansCL=out3
LSMeansDiffCL=out4;
```

```
proc glm data=dat1 plots=none;
  class trt;
  model DAVG = trt base / solution;
  lsmeans trt / stderr cl pdiff;
run;
ods output close; quit;
```

29) SAS code for CMH test and estimates with stratification factors adjustment:

```
proc freq data=dat1;  
  tables strat1*strat2*strat3*trt*Y/ list cmh;  
ods output cmh=cmhpval CommonRelRisks=risk;  
run;
```

30) Renal and hepatic adverse events include preferred terms from search term list 'Acute Renal Failure (SMQ)' and search term list 'Acute and non-infectious liver events' MedDRA 25.0.

31) Vital signs, and SCr collected after Day 29, PCR collected after day 44 will be assigned to "Post Day 29".

CCI [REDACTED]

33) For coagulation laboratory tests, both local and Covance lab records are collected in the data. In a visit where both Covance and local lab records are collected, Covance records will be picked over local lab records.

34) Reference ranges are based on Covance laboratory reference ranges.

35) COVID-19 medications include the following drugs:

Drug name
Chloroquine

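### The prespecified renal and hepatic adverse event groups are only listed; in the visible text no by-arm count of participants is planned for either group

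*SAP*

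**What the plan says.** SAP 7.1.6 closes with two sentences on event groups of interest. For the renal and hepatic groups: "Listing of renal and hepatic adverse events will be provided". For hypersensitivity: "Hypersensitivity including infusion-related reactions adverse events will also be summarized and listed".

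Both groupings are defined in SAP Appendix 2. Item 36 prints the hypersensitivity terms. Item 30 begins "Renal and hepatic adverse events include preferred terms from search term list" and names two lists under MedDRA 25.0: Acute Renal Failure (SMQ), and one for acute and non-infectious liver events. The terms inside those two lists are not printed.

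The same section plans general tables: "The number and percentage of participants who experienced at least 1 TEAE will be provided and summarized by SOC, High level term (HLT), PT, and" (the sentence ends by naming the arms). It repeats them by system organ class (SOC) and preferred term (PT) for Grade 3 or higher, drug-related, serious and discontinuation events. The counting rule is "Multiple events will be counted only once per participant in each summary".

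Protocol 8.2.1.1 says that the data for the first data monitoring committee (DMC) meeting "will include safety data, including renal and hepatic toxicity".

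**The concern.** Safety and tolerability in patients with severely reduced kidney function is a stated secondary objective. Protocol 1.3 traces the existing dosing restriction mainly to an excipient that is cleared by the kidney and accumulates when kidney function falls. It adds that the mechanism of the tubular injury seen in nonclinical studies is not understood. Renal and hepatic toxicity are the two toxicities named for the first DMC review. It is odd, then, that hypersensitivity gets a by-arm summary while these two groups, with definitions already written, get only a listing.

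At stake is a simple number that a reader of the study report will look for: how many participants in each arm had at least one event in the renal group, and how many in the hepatic group. If it is not a planned output, someone will either count it from the listing after unblinding or approximate it from rows that measure something slightly different.

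**Working it through.** The point concerns which outputs are planned. The plan states no figure to reproduce, so the check is a comparison of outputs.

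**1. What is planned for each group**

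| Event group | Definition | Listing | By-arm participant count for the group |
|---|---|---|---|
| Hypersensitivity, including infusion reactions | Appendix 2 item 36 | Yes | Yes (SAP 7.1.6) |
| Renal | Appendix 2 item 30 | Yes | None in the visible text |
| Hepatic | Appendix 2 item 30 | Yes | None in the visible text |

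**2. Can the group count be recovered from the planned adverse event tables?**

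- *PT rows.* Let n_j be the participants in one arm with at least one event under term j of a list. A participant with two of the terms is counted in both rows. The group count G therefore satisfies max(n_j) ≤ G ≤ Σ n_j. The sum equals G only if no participant has more than one of the terms, and the tables do not show that overlap.
- *SOC and high-level term (HLT) rows.* These do count each participant once within the row, so they are genuine participant-level aggregates. They follow the MedDRA hierarchy, however, and item 30 follows search lists. The documents do not print the lists, so a match can be neither shown nor excluded.
- *The listing.* G could be counted by hand, but it would not be a prespecified table. The sentence also does not restrict the listing to treatment-emergent events.

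**3. Do the other renal and hepatic outputs give it?**

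- Graded creatinine, ALT, AST and bilirubin abnormalities are tabulated by arm (SAP 7.2.2.2; Appendix 2 item 20). These are laboratory outcomes, not adverse event rates. SAP 7.2 itself recognises that renal replacement therapy (RRT) distorts creatinine and adds a sensitivity analysis for that reason.
- RRT-free days are compared by arm in participants without end-stage kidney disease (ESKD) at baseline (SAP 6.2.1). Death also lowers that count. In the safety section, RRT is only listed (SAP 7.5).

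None of these is the group count.

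**4. Why a renal row without baseline ESKD is useful**

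With a fraction f of participants having ESKD, the overall renal rate is (1 − f) × p(non-ESKD) + f × p(ESKD). Protocol 5.1.1 caps f at 20%. If that cap held among those treated and ESKD participants contributed no events (both assumptions), the overall rate would be 0.80 × p(non-ESKD). The dilution is modest and easily removed, because kidney disease status is already derived (Appendix 2 item 15).

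**5. What an interval on the new row would offer**

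SAP 2.2 says that enrolment stopped before 50% of plan. Half of 1116 is 558, so at most 557 were enrolled. With 2:1 allocation and the same assumed rate p in both arms, the 95% half-width for a difference is 1.96 × √[p(1 − p)(1/n₁ + 1/n₂)]. The rates and the two smaller totals are assumptions:

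| Total N | p = 5% | p = 10% | p = 20% |
|---|---|---|---|
| 557 | 3.8 points | 5.3 | 7.0 |
| 300 | 5.2 | 7.2 | 9.6 |
| 150 | 7.4 | 10.2 | 13.6 |

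The row would be descriptive. It would not settle whether a small excess exists.

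**The case against.** The strongest reply is that by-arm renal and hepatic evidence is already plentiful. All treatment-emergent events appear as participant counts by SOC, HLT and PT. Severe, related, serious and discontinuation events follow by SOC and PT. Graded laboratory abnormalities are by arm. Liver threshold counts are planned in SAP 7.2.3, although that sentence does not name treatment group. Laboratory changes are compared by Wilcoxon test, and RRT-free days are compared by arm. Adverse event tables by kidney disease status are allowed as an option. All of this stands. A reader might infer from the listing-only sentence that no renal or hepatic event rate can be compared between arms, or that an excess would go unseen. The documents do not support either reading.

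A reader might also infer a departure from the protocol. There is none: Protocol 8.6.2 asks for treatment-emergent events by SOC and PT, and the SAP meets and exceeds that. Nor does the DMC sentence in Protocol 8.2.1.1 bind the final tables. It describes a meeting that, per SAP 2.2, has already taken place, with details in the DMC charter. It shows that these toxicities are a named safety focus, not that they are the main one. Protocol 1.3 also reports that drug-related kidney injury was not observed clinically in the trials it cites.

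Finally, parts of the SAP are blacked out. Appendix 2 item 17 defines peak creatinine through Day 29, yet no visible section uses it, so some renal analysis probably sits in redacted text. The statement must therefore be limited to the visible text. These replies narrow the point, but none of them supplies the group count.

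**Conclusion.** The point holds in a limited form. In the visible text, the renal and hepatic groups of Appendix 2 item 30 have a listing and no by-arm participant count, whereas hypersensitivity has both. The planned PT rows cannot be summed to the group rate, and the documents do not show that any SOC or HLT row equals it.

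The consequence is small. Efficacy inference and Type I error are untouched, and the plan already contains substantial by-arm renal and hepatic information. The improvement is worth making because the outcome bears on a stated objective and its definition already exists. The conclusion rests on two conditions: that no redacted section contains the table, and that the item 30 lists do not happen to coincide with a single SOC or HLT row. Neither can be checked from the documents.

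**What to change.** Replace the listing sentence in SAP 7.1.6 with wording such as: *Treatment-emergent renal and hepatic adverse events (Appendix 2 item 30) will be summarized by treatment group in the Safety Analysis Set as number and percentage of participants with at least one event, separately for the renal and hepatic lists and counting each participant once per list, and listed. The renal row will also be shown excluding participants with ESKD at baseline.*

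A risk difference with 95% confidence interval is optional. The SAP plans none for any other adverse event category, so parity with hypersensitivity requires only the counts and percentages.

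The cost is one extra table, built from term lists and a kidney disease variable that the SAP already defines. It needs no new data.

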7.2. Laboratory Evaluations

Laboratory data collected during the study will be analyzed and summarized using both quantitative and qualitative methods. Summaries of laboratory data will be provided for the Safety Analysis Set and will include data collected up to the last dose of study drug plus 30 days. The analysis will be based on values reported in conventional units. When values are below or above the LOQ, they will be listed as such, and the closest imputed value will be used for the purpose of calculating summary statistics as specified in Section 3.7.

Because RRT may significantly impact certain lab values such as SCr and BUN, a sensitivity analysis will be conducted, in which records and/or participants may be excluded from analysis as follows:

- SCr and BUN will only be analyzed for participants who are not on RRT at baseline. If RRT is used during the study, any records from RRT start to end + 3 days will be excluded from analysis.

RRT started within 3 days before first dose is considered RRT at baseline.

Anticoagulation medications can impact coagulation lab parameters, such as aPTT, PT, and INR. Sensitivity analysis will be conducted for coagulation lab parameters. Any coagulation lab records under the influence of these medications will be excluded from analysis. For anticoagulation medications in the Warfarin class, coagulation lab records with a date in between the start and 5 + the stop date of the medication will be excluded; for other anticoagulation medications, records with a date in between the start and 1 + the stop date of the medication will be excluded.

A by-participant listing for laboratory test results will be provided by participant ID number and visit in chronological order for hematology, coagulation, serum chemistry, CCI [REDACTED] Values falling outside of the relevant reference range and/or having a severity grade of 1 or higher on the DAIDS Grading Scale (see Section 7.2.2) will be flagged in the data listings, as appropriate.

7.2.1. Summaries of Numeric Laboratory Results

Descriptive statistics will be provided by treatment group for selected laboratory test specified in the study protocol as follows:

- Baseline values
- Values at each postbaseline analysis visit
- Change from baseline at each postbaseline analysis visit
- Percentage change from baseline to each postbaseline analysis visit (if specified)

A baseline laboratory value will be defined as the last nonmissing measurement obtained on or prior to the date/time of first dose of study drug. Change from baseline to a postbaseline visit will be defined as the visit value minus the baseline value. The mean, median, Q1, Q3, minimum, and maximum values will be displayed to the reported number of digits; SD values will be displayed to the reported number of digits plus 1. Baseline and change from baseline will be compared between the treatment groups using the 2-sided Wilcoxon rank sum test.

In the case of multiple values in an analysis window, data will be selected for analysis as described in Section 3.8.3.

In an analysis window (including baseline window), if both central lab and local lab results are available, then central lab results will be used instead of local lab results; local lab results will only be used if central lab results are missing.

7.2.2. Graded Laboratory Values

The DAIDS Table for Grading the Severity of Adult and Pediatric Adverse Event, Version 2.1 (July 2017) (see Section 7.1.2) will be used for assigning toxicity grades (0 to 4) to laboratory results for analysis. Grade 0 includes all values that do not meet the criteria for an abnormality of at least Grade 1. For laboratory tests with criteria for both increased and decreased levels, analyses for each direction (i.e., increased, decreased) will be presented separately.

For baseline, if both central lab and local lab results are available, then central lab results will be used to determine baseline toxicity grade; local lab results will only be used if central lab results are missing. For postbaseline laboratory abnormalities, both central lab and local lab results will be used.

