— For continuous data:

- CCI [REDACTED]
- For other continuous data, the average of the measurements will be taken.

— For categorical data:

- For SARS-CoV-2 infection status, the highest severity (ie, a positive PCR result) will be selected.
- For other categorical data, the lowest severity will be selected.

For the 8-point ordinal scale, only Screening and Day 1 predose values will be considered for baseline value selection.

[REDACTED]

[REDACTED]

[REDACTED]

CC
[Redacted]

[Redacted]

[Redacted]

[Redacted]

[Redacted]

[Redacted]

In an analysis window (including baseline window), if both central lab and local lab results are available, then central lab results will be used for record selection instead of local lab results; local lab results will only be used for record selection if central lab results are missing.

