7.2.2.1. Treatment-Emergent Laboratory Abnormalities

Treatment-emergent laboratory abnormalities are defined as values that increase at least 1 toxicity grade from baseline at any postbaseline time point, up to and including the date of last dose of study drug plus 30 days. If the relevant baseline laboratory value is missing, any abnormality of at least Grade 1 observed within the time frame specified above will be considered treatment emergent.

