7.2.2.2. Summaries of Laboratory Abnormalities

Laboratory data that are categorical will be summarized using the number and percentage of participants in the study with the given response at baseline and each scheduled postbaseline visit.

The following summaries (number and percentage of participants) for treatment-emergent laboratory abnormalities will be provided by lab test and treatment group; participants will be categorized according to the most severe postbaseline abnormality grade for a given lab test:

- Treatment-emergent laboratory abnormalities
- Treatment-emergent Grade 3 or 4 laboratory abnormalities

For all summaries of laboratory abnormalities, the denominator is the number of participants with nonmissing postbaseline values up to 30 days after last dosing date.

A by-participant listing of treatment-emergent Grade 3 or 4 laboratory abnormalities will be provided by participant ID number and visit in chronological order.

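### Baseline toxicity grades come from the central laboratory when it has a result, but post-baseline grades come from both laboratories, so an abnormality present before dosing can be counted as treatment-emergent

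*SAP*

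**What the plan says.** SAP 7.2.2 sets two different rules for graded laboratory results. When both laboratories have a baseline result, "then central lab results will be used to determine baseline toxicity grade; local lab results will only be used if central lab results are missing". After baseline, "For postbaseline laboratory abnormalities, both central lab and local lab results will be used".

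The graded tables then apply two further rules. In 7.2.2.1, "Treatment-emergent laboratory abnormalities are defined as values that increase at least 1 toxicity grade from baseline at any postbaseline time point", up to 30 days after the last dose. In 7.2.2.2, "participants will be categorized according to the most severe postbaseline abnormality grade for a given lab test".

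The numeric summaries work differently. SAP 7.2.1 says "A baseline laboratory value will be defined as the last nonmissing measurement obtained on or prior to the date/time of first dose", and both 7.2.1 and 3.8.3 give central results priority in every analysis window, baseline included: "local lab results will only be used for record selection if central lab results are missing". The same laboratory therefore has priority before and after dosing.

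On which tests have two sources, Appendix 2 item 33 says "For coagulation laboratory tests, both local and Covance lab records are collected in the data". It goes on to say that where a visit has both, the Covance (central) record is chosen. No such statement is made for chemistry or hematology. Protocol 8.6.3 defines treatment-emergent laboratory abnormalities but gives no rule on laboratory source.

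**The concern.** A treatment-emergent grade is a comparison of after with before. If one laboratory supplies the "before" and the worse of two supplies the "after", a participant can cross a grade boundary because a second source was admitted, with no change in the patient.

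For example, central and local samples on the same pre-dose day read Grade 0 and Grade 1, and the local value is still Grade 1 after dosing. The baseline grade is 0, the worst post-baseline grade is 1, and the participant is counted. The local result that shows the abnormality was already there has been set aside.

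Treatment-emergent laboratory abnormalities are one of the protocol's stated safety criteria, and safety in severely reduced kidney function is an open question for this trial. Spurious events in both arms raise both rates and can make a real laboratory effect harder to see.

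**Working it through.** The plan gives no figure on this point, so there is none to reproduce. The check has three steps.

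**1. The rule itself.** Let C and L be the pre-dose central and local grades (0 to 4), both unchanged after dosing. Under 7.2.2 the baseline grade is C and the worst post-baseline grade is max(C, L). The participant is flagged if max(C, L) > C, that is, if L > C. Of the 5 × 5 = 25 combinations, 4 + 3 + 2 + 1 = 10 are flagged. If both sources count at baseline, the condition becomes max(C, L) > max(C, L), and 0 of 25 are flagged. So the miscount follows from the rule, but only where L > C.

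**2. Size among participants with both sources.** All inputs here are assumptions, because the documents give none:
- grade cuts at 1.1, 1.25, 1.5 and 3.0 × ULN
- true values lognormal, between-person SD 15%, no true change
- between-laboratory SD 0, 5 or 10%; within-person SD 3 or 5%
- four post-baseline samples per source

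The simulated share scored treatment-emergent, with median value 0.98 × ULN, is:

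| Between-lab SD | Within-person SD | SAP rule | Both sources at baseline | Excess (points) |
|---|---|---|---|---|
| 0% | 3% | 13.6% | 9.5% | 4.1 |
| 0% | 5% | 23.3% | 17.2% | 6.1 |
| 5% | 3% | 18.1% | 10.8% | 7.3 |
| 5% | 5% | 26.7% | 18.7% | 8.0 |
| 10% | 3% | 24.9% | 12.2% | 12.7 |
| 10% | 5% | 32.1% | 20.3% | 11.8 |

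Moving the median to 0.85 × ULN, further from the Grade 1 cut, reduces the excess to about 1 to 5 points (for example 3.9 − 2.9 = 1.0 and 9.6 − 4.7 = 4.9). The full range is therefore about 1 to 13 points.

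Over all participants, the excess is f × (excess among those with both sources), where f is the unknown share with both. For f from 0.25 to 1.0 (assumed), this runs from 0.25 × 1.0 = 0.25 points to 1.0 × 12.7 = 12.7 points per test.

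**3. Effect on a comparison.** If a proportion a of participants without a true event is falsely flagged in each arm, an observed rate is p + (1 − p)a. Take true rates of 20% and 10% (ratio 2.0, difference 10 points), with illustrative values of a:

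| a | Arm 1 | Arm 2 | Ratio | Difference (points) |
|---|---|---|---|---|
| 0.03 | 0.20 + 0.80 × 0.03 = 0.224 | 0.10 + 0.90 × 0.03 = 0.127 | 1.76 | 9.7 |
| 0.05 | 0.240 | 0.145 | 1.66 | 9.5 |
| 0.09 | 0.272 | 0.181 | 1.50 | 9.1 |

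The ratio is diluted noticeably and the difference only slightly.

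**The case against.** The case against giving this much weight has several sound parts.

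- **Coagulation is the only test with confirmed dual records, and item 33 limits the problem there.** Its preference for Covance is not restricted to baseline, so on that reading same-visit local results drop out after dosing too. This stands. What remains for coagulation is a conflict between item 33 and 7.2.2, plus visits with a local result only.
- **For chemistry and hematology, two sources are not shown.** The protocol synopsis and section 6.5 refer to local practice and standard of care, and the schedule footnotes name the central laboratory only for coagulation. Where one source exists, the rule does nothing.
- **The size depends on chosen inputs.** A median of 0.98 × ULN puts the population beside the first cut. With no between-laboratory difference, the 4 to 6 point excess arises only because the comparator uses two baseline draws instead of one. Much of the false rate remains after the change, because it comes from taking the worst of eight post-baseline values.
- **The harm is bounded.** SAP 7.2.2.2 plans counts and percentages by arm, not risk ratios, and the by-participant listings would show the pre-dose local values.

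A reader might infer that an old central screening value will routinely displace a later local one. The documents do not support this for coagulation: a central sample is scheduled again on Day 1, and Day 1 assessments must precede dosing, so that pattern needs the scheduled sample to be missing.

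None of this removes the mismatch in 7.2.2. The sensitivity analyses in 7.2 exclude records for RRT or anticoagulant use, not by laboratory source.

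**Conclusion.** The concern holds as a conditional one. SAP 7.2.2 uses different sources before and after dosing, and no other text corrects this for graded results. A false treatment-emergent count needs three things together: both sources present, a pre-dose local grade above the central grade, and recurrence of that grade in a local result after dosing. A pre-dose abnormality that the central result shows at the same grade is not miscounted, so it would be wrong to read the rule as turning pre-dose abnormalities into events in general.

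The excess is about 1 to 13 points among participants with both sources, under the assumed cuts and noise. The trial-level size cannot be stated, because f and the between-laboratory difference are not in the documents. The same rule applies in both arms, so the expected effect is inflated rates and some dilution, with no favour to either arm. The primary and key secondary efficacy analyses are not affected.

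A reader might also infer that the baseline rules in 3.8.3 and 7.2.1 share the fault. They do not: central priority applies there in every window. Admitting a later local baseline against central post-baseline values would create the mixed-laboratory comparison that should be avoided.

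The change is worth making because it is cheap and the affected output is a safety table, but it is not critical to the trial's conclusions.

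**What to change.** Change SAP 7.2.2 only:

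1. Set the baseline toxicity grade to the highest grade among central and local results from the last pre-dose sampling day. Keep the post-baseline rule, so both sources count on both sides of the first dose.
2. Add a treatment-emergent table that uses central results only, before and after dosing, as a sensitivity analysis.
3. Reconcile Appendix 2 item 33 with 7.2.2, stating whether same-visit local coagulation results count after baseline in the graded tables.

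Leave the numeric-summary rules in 3.8.3 and 7.2.1 unchanged.

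The cost is a wording change, one derivation and one extra table, with no new data. There is a statistical price: a worst-of-both baseline is slightly less sensitive to small true rises. For a true 10% rise under the same assumptions, detection falls by about 1 to 6 points. The central-only table does not use a worst-of-both baseline and so gives a check on that loss. The change should be made before unblinding; after SAP finalization, the SAP's introduction requires it to be documented in the study report.
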